Assessing Acceptability, Cost, and Efficacy of STELLA-Support via Technology: Living and Learning with Advancing AD

01/31/2022

NCT04335110

Protocol Title:

Assessing Acceptability, Cost, and Efficacy of STELLA-Support via Technology: Living and Learning with Advancing AD

Objectives

STELLA (Support via TTechnology: Living and Learning with Advancing Alzheimer's disease and related dementias) is a multicomponent video-conference based intervention designed to facilitate effective management of behavioral and psychological symptoms of dementia (BPSD). In the STELLA intervention, professionals ("Guides") meet with family members ("Care Partners") caring for persons with dementia. Working together, the Care Partners and Guides identify strategies to address upsetting behaviors in the moderate to late stages of dementia. The goal of this intervention is to reduce upsetting behaviors and thus care partner burden including costs.

The specific aims of this study are:

Phase 1

1. Using quantitative and qualitative approaches, assess feasibility and participant acceptability of (a) STELLA, and (b) the assessment methods (subjective measures and unobtrusive objective monitoring).
2. Using quantitative strategies, assess the preliminary effect of STELLA on (a) the affective impact of caregiving, Care Partner cognitive function and person with dementia quality of life, and on (b) Care Partner and person with dementia objective digital behavioral biomarkers (activity, sleep and time together).
3. Test the feasibility of employing digital behavioral biomarker data, combined with qualitative Care Partner feedback, to assess mechanisms of behavior change before, during and after the STELLA intervention.

Phase 2

1. Quantify the costs of delivering the STELLA intervention.
2. Quantify the cost efficacy of STELLA in relation to BPSD frequency and CP reactivity and assess the relationship between costs, BPSD, and care partner burden.

H1: There is a relationship between BPSD and cost: More BPSD behaviors and more CP reactivity to the BPSD are associated with higher out-of-pocket and implicit costs for families living with dementia.

H2: There is a relationship between out-of-pocket and implicit costs and objective measures of burden identified in the ORCASTRAIT Living Lab continuous home assessment. Higher objective burden will correlate with higher implicit and out-of-pocket costs.

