a. Care Partners and Persons with Dementia. Up to 40 Care Partners and their 40 care-recipients with ADRD will participate in this study. The primary focus of this study is on Care Partners, however, we will gather subjective and objective data on participants with ADRD to assess the effect of the intervention on Care Partner affective responses to caregiving and quality of life for both. STELLA participants will be recruited from the existing cohort of patients, and their Care Partners, who are enrolled in the ORCASTRAIT Life Laboratory (OSLL).

There has been no pilot testing of STELLA with non-English speaking care partners, and all materials have been tested in English. Therefore, only English-speaking participants are included in STELLA.

b. Inclusion and exclusion criteria. The research team will assess eligibility of interested parties based on the criteria listed in Table 1. In the event of a screen failure, data collected during screening will be destroyed at the end of the study. The recruitment team will track the number of care partners contacted for the study, the number consented, the number of those that dropped out and the number of those that completed the entire intervention.

Table 1: Inclusion/Exclusion Criteria

Participant	Inclusion	Exclusion
Care Recipient	
 Diagnosis of ADRD, moderate to late stages Exhibits 2 or more behaviors listed on RMBPC¹⁶ that are bothersome to the Care Partner and occur 3 or more times/week at study enrollment Family member of Care Partner (this can be a relative, spouse or close kin that is considered family) 	
 Dementia not related to ADRD Unable to leave Care Partner during Partner training Early stage dementia, as defined by MoCA of about 15/30 or higher.

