Intervention (4 weekly sessions)	Meet with for 4 weekly sessions, beginning with Session 1 . (see Table 2)	After Mercury Baseline survey completed
Starlet Survey (Survey 2)	Electronic assessment of depression, burden	1 month after Session 1
Intervention (4 weekly sessions)	Meet with Guide and up to 4 other Care Partners for 4 more weekly sessions (See Table 2)	After session #8
Venus Survey (Survey 3)	Full assessment, including program survey	2 months after Session 1
Post-STELLA Assessment	Complete personalized target problem assessment via Qualtrics or via video or phone call with a Research Assistant	After Venus survey completed
Focus Groups	Optional focus group to provide study team with feedback	After Venus survey completed
Earth Survey (Survey 4)	Full assessment (Table 4)	6 months post-intervention
Earth Survey (Survey 5)	Full assessment (Table 4)	12 months post intervention
ORCASTAIT Surveys	Cost, burden as described in ORCASTRAIT Protocol	Weekly, while in ORCASTRAIT

Phase 1

Measures. Aim 1: Feasibility will be assessed by measuring how many Care Partners who start the program successfully complete it. Care Partners will fill out our telehealth survey that asks them about acceptability.^(23, 24) Acceptability will also be assessed qualitatively using focus groups.⁽²⁵⁾ The focus groups will be conducted via videoconferencing and will be recorded and transcribed for analysis.^(15, 16)

Aim 2: Standard quantitative measures that were used in the earlier pilots^(15, 16) will be used to provide preliminary evidence for efficacy. The quantitative measures are grouped into 5 surveys: Mercury Baseline, Starlet, Venus, Earth (6 months post intervention) and Earth (12 months post intervention). Along with the ORCASTRAIT Living Lab suite of measures (demographics, activity, time with person with dementia, sleep-related behaviors), we assess burden using the RMBPC⁽²⁶⁾ and the 22-item Zarit Burden Interview (ZBI). To provide focus for the intervention, each Care Partner will identify and rate 2-3 specific target problems to address in STELLA. Pre-death grief will be assessed with the Marwit Meuser Caregiver Grief Index, Short Form (MMCGI-SF).⁽²⁷⁾ Care Partner plans for person with dementia placement will be assessed with the

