revised Desire to Institutionalize (DTI) scale.⁽²⁸⁾ Care Partner depression will be measured with the CESD-10⁽³⁰⁾ and role captivity will also be assessed.⁽³¹⁾ In addition to subjective assessments, we will evaluate the effect of STELLA on digital behavioral biomarkers (activity, time spent together and sleep) obtained from the ORCASTRAIT platform. Total daily activity, time together and alone, and sleep duration, will be assessed prior to, during, and after the intervention. Care Partners will complete all assessments electronically. A secure link to each assessment will be emailed to each CP. We will ask the CPs to complete the assessments within 5 days of receiving the email. If they do not, we will call them to assess their situation. If they do not complete surveys as outlined on the times listed in Table 3 they may not continue with the intervention.

Aim 3. To identify which components of STELLA are most helpful to Care Partners, we will assess the mechanisms of action for reducing burden, depression and grief and improving cognitive function and sleep. Care Partners will complete the surveys (**Table 3**) before the intervention, after Session 4 and after the intervention. An analysis of objective data (**Figure 1**) will also be done during the intervention. We will ask Care Partners in our focus groups to report what they found most helpful about STELLA.

Table 4: Subjective Assessment Descriptions

Measure	Description
Mercury Baseline	
Demographics	Demographics, including hours/week caregiving
Revised Memory & Behavioral Problems Checklist (RMBPC) ²³	Measure of frequency and reactivity to behavioral and psychological symptoms of dementia ²³
Personalized target problem assessment	Care partner-identified targeted problem assessment
Zarit Burden Interview (ZBI) ³³	4-item measure of burden
Center for Epidemiologic Studies Depression Scale (CESD-10) ³⁴	10-item depression measure
Marwit Meuser Caregiver Grief Index-Short Form (MMCGI-SF) ³⁵	Care partner pre-death grief ³⁵
Placement plan scale ³⁷	One-item assessment of plans for placement for family member with dementia ³⁷
QoL AD ³⁶	13-item assessment of quality of life for both the care partner and the person with dementia.
Starlet Survey	
ZBI ³³	
CESD-10 ³⁴	
Venus Survey	
RMBPC ²³	
 • See Baseline for descriptions • Baseline: 
 + STELLA contact survey + Experience Survey -Demographic survey
Personalized target problem assessment	

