Other quantitative analyses may be performed if they data reveal important trends.

PHASE 2

Aim 1: We will carry out a costing of the intervention to determine implementation costs of STELLA.

[figure not shown]

Figure 1: Composite model spider plot of digital behavioral biomarkers in a dyad showing potential domains associated with the degree of caregiver burden (49). Numbers are odds of having the behavior relative to low burden. Similar comparisons can be made relative to baseline (e.g. sleep time or time alone before relative to after intervention).

Aim 1 Anticipated Results and Implications. The costing will demonstrate the actual costs of delivering the intervention. This is essential for future pragmatic trials and ultimately for widespread adoption in the US health system.

Aim 2: Assess data collected from CPs for correlations between BPSD frequency and explicit costs to measure the direct cost impact of the intervention. We then assess the relationship between BPSD frequency, CP reactivity, and out-of-pocket costs for families using linear regression models and controlling for salient covariates based on preliminary correlational analysis. We will repeat this analysis for implicit costs. We will then compare both the explicit and implicit out-of-pocket costs for participating CPs to those who do not participate.

Aim 2 Anticipated Results and Implications. We expect to see a relationship between BPSD and cost. Specifically, more BPSD behaviors and more CP reactivity to the BPSD will be associated with higher out-of-pocket and implicit costs for families living with dementia. Further, we expect to find a relationship between out-of-pocket and implicit costs and objective measures of burden identified in the ORCASTRAIT Living Lab continuous home assessment. Higher objective burden will correlate with higher implicit and out-of-pocket costs. This will provide much needed data on the intervention's cost-efficacy compared to other interventions to support people living with dementia.

6. Data and Specimens.

No genetic material or specimens will be collected in this study.

a. Sharing of Results with Subjects

Results of the RMBPC and the Pre-Treatment Survey will be shared with the Care Partner prior to the intervention. This will help the Care Partner identify behaviors they want to target in the training sessions. If the memory, depression, burden or grief scores are abnormal, the Care Partner may be

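### Phase 2 Aim 2 relates BPSD to cost with no dyad term, clustering or cost window, so the result can describe H1's across-family association but cannot support a statement on STELLA's cost impact

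*Combined protocol and SAP*

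**What the plan says.** The protocol is also the analysis plan, and the Phase 2 Aim 2 paragraph of the Analytic Plan (section 5) contains the whole method.

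- **Correlation step.** Data from Care Partners are assessed for "correlations between BPSD frequency and explicit costs to measure the direct cost impact of the intervention".
- **Regression step.** "We then assess the relationship between BPSD frequency, CP reactivity, and out-of-pocket costs for families using linear regression models", "controlling for salient covariates based on preliminary correlational analysis". For the second cost type: "We will repeat this analysis for implicit costs".
- **Hypothesis.** H1 in the Objectives reads "More BPSD behaviors and more CP reactivity to the BPSD are associated with higher out-of-pocket and implicit costs for families living with dementia".
- **Predictor.** Table 4 describes the RMBPC as "Measure of frequency and reactivity to behavioral and psychological symptoms of dementia". It is listed for Mercury Baseline, Venus and the Earth assessment, and Table 3 gives Earth at 6 and at 12 months after the intervention. Starlet holds only the ZBI and CESD-10. That makes four RMBPC readings per dyad.
- **Outcome.** Out-of-pocket costs come from an item added to the parent study's online survey, which Table 3 schedules as "Weekly, while in ORCASTRAIT". Implicit cost is average weekly care hours multiplied by a single wage of about $29.
- **Size.** Section 4a: "Up to 40 Care Partners and their 40 care-recipients with ADRD will participate in this study".

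The paragraph does not state the unit of analysis, which weeks of cost go with which RMBPC reading, or any dyad effect, change score or clustering. By contrast, Phase 1 Aim 2 does specify changes in scores over time.

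**The concern.** Two questions can be asked of these data. Do families with more BPSD spend more than other families? Does a given family spend more when its own BPSD rises? H1 as worded asks the first. A statement on what STELLA does to cost needs the second, because STELLA is meant to act by lowering BPSD and reactivity within a family. The plan uses one set of correlations and regressions and does not separate the two.

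A family's usual spending depends on lasting features that have nothing to do with whether its BPSD rises or falls. If those features happen to run with BPSD level, the across-family slope contains them. They can produce a slope where no within-family relation exists, or cancel one that does. Selecting covariates by correlation removes only the part that is measured and selected.

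There is also a question of precision. If the four readings per dyad are stacked in an ordinary regression, up to 40 × 4 = 160 rows are treated as independent although they come from 40 families. The standard errors are then too small.

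What is at stake is the inference drawn for the next stage. The plan expects this analysis to inform the cost-efficacy of STELLA, and an across-family slope could mislead in either direction.

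**Working it through.** The documents give no alpha, power, variance or intraclass correlation for the cost analyses, so there is no figure of the plan's own to reproduce. The inputs below are assumptions, except 40 dyads and 4 dates.

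**Setting.** BPSD *x* has variance 1, of which a share *k* (0.5 or 0.7) lies between dyads. Cost *y* has residual variance 1, of which 0.6 lies between dyads. A stable family feature has coefficient *g* = 0.5 on cost and correlation *r* with the dyad's stable BPSD level. The true within-dyad slope is *b*. Three regressions are compared: stacked readings with no dyad term, one mean per dyad, and within-dyad (dyad fixed effects). In a balanced linear model with one predictor, the slope on the within-dyad deviation is the same as the fixed-effects slope.

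**Step 1: expected slope.**
- Stacked: *b* + *g r* √*k*
- Dyad means: *b* + *g r* √*k* / [*k* + (1 − *k*)/4]
- Within-dyad: *b*

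| Case | *k* | Stacked | Dyad means | Within-dyad |
|---|---|---|---|---|
| *b* = 0, *r* = +0.3 | 0.5 | 0.15 × 0.707 = 0.106 | 0.106/0.625 = 0.170 | 0 |
| *b* = 0, *r* = +0.3 | 0.7 | 0.15 × 0.837 = 0.125 | 0.125/0.775 = 0.162 | 0 |
| *b* = 0.2, *r* = −0.5 | 0.5 | 0.2 − 0.177 = 0.023 | 0.2 − 0.283 = −0.083 | 0.2 |
| *b* = 0.2, *r* = −0.5 | 0.7 | 0.2 − 0.209 = −0.009 | 0.2 − 0.270 = −0.070 | 0.2 |

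A simulation of 3,000 runs per case agrees. With *b* = 0 and *r* = +0.3, the mean slopes were 0.104 and 0.123 (stacked), 0.168 and 0.161 (dyad means) and 0.001 (within-dyad). The share of runs with p < 0.05 was 33% and 42% stacked, 16% and 19% on dyad means, and about 5% within-dyad.

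**Step 2: stacking without clustering, no confounder, no effect.** The variance of the slope is understated by a factor of about 1 + 3 × *k* × 0.6.
- *k* = 0.5: factor 1.90, square root 1.378; the nominal 1.96 cut-off acts as 1.96/1.378 = 1.42, so two-sided error is about 16%.
- *k* = 0.7: factor 2.26, square root 1.503; 1.96/1.503 = 1.30, so error is about 19%.

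The simulation gave 16% and 19%.

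**Step 3: what the within-dyad slope can detect.** SE = √[0.4 / (40 × 3 × (1 − *k*))].
- *k* = 0.5: √(0.4/60) = 0.082; for *b* = 0.2 the ratio is 2.45 and power about 69% (simulated 67%).
- *k* = 0.7: √(0.4/36) = 0.105; ratio 1.90, power about 48% (simulated 46%).

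With no confounder and the same *b*, simulated power on dyad means was 20% and 25%. With one value per dyad, the correlation detectable with 80% power is tanh[(1.96 + 0.84)/√37] = 0.43.

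**Step 4: a second set of assumptions.** Take log-cost SD 1.0 between and 0.6 within dyads, and BPSD SD 0.8 between and 0.5 within. With a stable correlation of 0.3 to 0.5 and no within-dyad effect, the slope runs from 0.3 × 0.8/0.89 = 0.27 (stacked) to 0.5 × 0.8/0.7025 = 0.57 (dyad means). Here 0.89 = 0.64 + 0.25 and 0.7025 = 0.64 + 0.25/4. Unclustered stacking rejects a true null in about 22% to 23% of studies. For a true slope of 0.3 without confounding, power is about 76% within-dyad and 33% on dyad means.

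**The case against.** The strongest reply is that H1 is an association across families, and a comparison of levels answers it. That stands. A reader might take the 16% to 42% rejection rates in Step 1 as false-positive rates for H1. They are not: in that setting families with more BPSD really do spend more, so H1 as worded is true. The rates count as error only for a within-family or cost-impact reading. The plan supplies that reading itself, in the correlation sentence, so the point does not rest on replacing H1.

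Other points that stand:
- The level comparison is inferred. It is the best-supported reading, since H1 is in levels and no change or dyad term appears, but the plan states no unit of analysis.
- A reader might infer that income and insurance go unmeasured. The documents do not show this: Table 4 lists demographics without items, and the parent study's protocol is not included.
- Local prices and insurance do not enter the valuation of implicit cost, because one wage is applied to all. Lasting differences in hours still do: Table 1 admits both co-resident Care Partners and those spending as little as 4 hours a week.
- A within-dyad slope removes only stable differences. When BPSD and cost were simulated to drift together within dyads (correlation 0.3 to 0.8, assumed), the within-dyad test rejected a true null in 10% to 79% of studies even with date terms.
- Survey-date terms absorb the average change after STELLA. The within-dyad slope is therefore not itself an estimate of the intervention's effect on cost. The planned comparison with non-participants is a separate analysis.
- Phase 1 Aim 2 calls the study exploratory, and Phase 2 sets no significance rule. That lowers the stakes, but an exploratory slope still needs a defined meaning.

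A reader might also infer that regression on raw dollars would give intervals with poor coverage. That depends on assuming multiplicative effects. With no effect and one row per dyad, ordinary regression covered 95% in a check with skewed costs and up to 20% zeros. The plan does not fix a cost scale.

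**Conclusion.** The concern holds in a limited form. The analysis as written can describe whether higher-BPSD families have higher costs. It cannot support the further use of that link as a measure of STELLA's cost impact, because stable family differences can create it or hide it. If readings are stacked without clustering, intervals are also too narrow, even for H1.

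In the main illustrative setting the distortion is about 0.10 to 0.17 for a modest confounder and 0.18 to 0.28 for a stronger one, in units where BPSD and residual cost each have variance 1. Unclustered stacking gives about 16% to 19% error at a nominal 5%, and about 22% to 23% under the second set of variances. These sizes rest on assumed variances, intraclass correlations and confounding strengths. The direction of the argument does not. The documents do not support the stronger conclusion that H1 itself would be falsely declared.

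This is worth changing because the data already planned allow a better analysis at little cost.

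**What to change.** Amend the Phase 2 Aim 2 paragraph as follows.

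1. **Cost window.** For each RMBPC date, average weekly cost over one fixed window that does not run into the STELLA sessions at baseline, for example a set number of weeks ending at the RMBPC date, where available. A window after Mercury would pair pre-intervention BPSD with costs probably incurred during sessions. A backward window at Venus will overlap the later sessions. The date term takes up the average of any session-related cost there, but the overlap should be acknowledged.
2. **Model.** Fit one model with BPSD frequency and reactivity each split into dyad mean and within-dyad deviation, plus survey-date terms, with dyad-clustered or bootstrap intervals.
3. **Reporting.** Give both slopes. The between-dyad slope answers H1 as worded. Only the within-dyad slope should inform any statement on cost impact, with the caveat that dyad-specific progression is not removed.
4. **Scale.** Add a log-link or similar model as a sensitivity analysis if costs are skewed.
5. **Implicit cost.** Apply the method only where hours are collected repeatedly. Hours per week sits in the baseline demographics, which later surveys drop, so this depends on the weekly time item.

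The cost is plan wording and modest programming, with no new instrument. Precision will be low if BPSD changes little within dyads, or if costs are missing at some dates. The documents do not show whether every dyad has cost data at all four.

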Care Partner	
 Adult caring for family member with ADRD Lives with care recipient OR spends at least 4 hours/week with care recipient⁽²¹⁾ Age of 18 years or older Speak English Own a computer/device with a reliable internet connection and compatible operating system 	
 Unable to find activity for care recipient during training which would allow Care Partner to work privately, one-on-one during training Completed similar telehealth intervention within the last year Hearing and vision problems severe enough to prevent participation Unwilling or unable to adequately follow study instructions and participate in study procedures
Both	Participate in ORCASTRAIT (IRB#20236)	

c. Vulnerable populations. The primary focus of this study is to assess the feasibility, costs, and efficacy of subjective and objective measurements of Care Partner and person with dementia responses to the STELLA intervention. Therefore, in order for this study to be successful, participants with moderate to late stage ADRD will be recruited. Few interventions address the needs of families in these later stages.

We will ask that a legally authorized representative (LAR) and, if appropriate, the person with ADRD, if the person with ADRD is competent to make a decision about participation. If the LAR and/or the person with ADRD are concerned about competency, the LAR will be asked to make the participation decision. No other vulnerable populations such as children, prisoners, or pregnant women will be included in this study. All Care Partners will be 18 or older.

d. Setting. This study will take place at OHSU. Participants will connect (from their homes or another convenient location) to the research team via direct-to-home, telehealth, video-conferencing and over the telephone at the Layton Aging and Alzheimer's Disease Center. Interventionists will meet with

caregivers via videoconferencing on an OHSU computer and HIPAA secure link. The interventionist may complete the visit from his or her home, OHSU office or other convenient private location. They will use a privacy screen so that participants will not see their home or office environments. No others (e.g., family members of interventionists) will be allowed in the room during the intervention. Please see ORCASTRAIT (IRB#20236) protocol for details of living lab.

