ZBI ³³	
CESD-10 ³⁴	
MMCGI-SF ³⁵	
Placement plan scale ³⁷	
QoL-AD	
STELLA contact	STELLA care partner contact post intervention
STELLA Experience Survey	16-item + comments on satisfaction, privacy, ease of use
Earth Assessment	
RMBPC ²³	
 • See Baseline for descriptions • Baseline: 
 + STELLA contact survey -Experience Survey
ZBI ³³	
CESD-10 ³⁴	
MMCGI-SF ³⁵	
Placement plan scale ³⁷	

QoL-AD	-Demographic survey
STELLA contact	

Phase 2

Aim 1. Quantify the costs of delivering the STELLA intervention. This will measure the direct costs of delivering the intervention (wage multiplied by time of all personnel supporting the intervention) as well costs of technology and equipment, and any in-kind donations of equipment or time to support the intervention.

Aim 2. Quantify the cost efficacy of STELLA in relation to BPSD frequency and CP reactivity and assess the relationship between costs, BPSD, and care partner burden.

Out-of-pocket costs for participating dyads will be collected using an addition to the weekly online ORCASTRAIT survey. CPs will be queried about personal funds spent on health care services, co-pays, medications, or equipment. CP time dedicated to these care-related activities will also be collected. Implicit costs for families will be calculated by multiplying the average weekly hours of care provided by the CP by the average hourly wage of paid caregivers in Portland, Oregon (approx. \$29).

Analytic Plan.

Phase 1

Aim 1: Feasibility will be assessed by calculating the proportion of enrolled Care Partners who completed the full intervention. Reasons for drop-out and discontinuation will be investigated carefully. Focus group transcriptions will be analyzed for themes of acceptability using narrative analysis.⁽²⁵⁾

Aim 1 Anticipated Results and Implication. We anticipate that the Care Partner will find the STELLA intervention feasible and acceptable. This will provide foundational information for future proposals.

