Aim 2: Efficacy will be assessed by calculating changes in the subjective scores before, during and after the intervention using linear regression models and controlling for age, sex and education. Since this is an exploratory (proof-of-concept) study with a small sample size, we do not expect statistically significant findings, but pre-post change and standard deviation of the change will be used to calculate the sample sizes for the next stage, a RCT (NIH Stage II⁽³²⁾, Phase 1) study.

Objective digital behavioral biomarker data collected from the ORCASTRAIT Living Lab (e.g., daily activity (steps), total sleep time, times together) will be assessed before, during and after the intervention and compared to subjective findings. Simple Spearman correlations will be used to explore the relationship of the objective continuous sensor-derived data to the subjective data, where the continuous objective digital data is collapsed to mean values which will serve as a point estimate prior to, during and after the intervention. We will compare the shift in the distribution of each of the digital behavioral biomarkers from baseline to identify relative changes during and after the intervention. We will compare the objective and subjective findings of the dyad to identify trends that correlate with burden (**Figure 1**)⁽³³⁾.

Aim 2 Anticipated Results and Implications. We anticipate that STELLA will reduce Care Partner burden and grief and improve family quality of life. These improvements in turn will decrease

Care Partner desire to place family members in long-term care. We expect these findings will be supported by both subjective and objective data.

Aim 3: Before Session 5, subjective and objective data (**Table 4**) will be compared to pre, mid- and post-intervention data to identify trends. Qualitative data will be gathered during the focus groups. Participants will be asked what they thought was most helpful about the intervention and what they thought of the format. The objective and subjective results will be used to identify which components of STELLA were most effective and which need to be modified to improve the potency of future iterations.

Aim 3 Anticipated Results and Implications. We expect to see an improvement in the objectives and subjective data, and we expect that we will need to revise the STELLA intervention. We will use information from the focus groups and the accrued data to revise as needed.

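### Covariates for the Phase 2 cost regressions are chosen by preliminary correlations in at most 40 dyads; a short fixed set including co-residence and excluding caregiving hours should replace the screen

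*Combined protocol and SAP*

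**What the plan says.** All references are to the combined protocol and SAP.

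- **Hypothesis (Objectives, Phase 2, H1):** "More BPSD behaviors and more CP reactivity to the BPSD are associated with higher out-of-pocket and implicit costs for families living with dementia".
- **Covariate rule (section 5, Analytic Plan, Phase 2 Aim 2):** linear regressions for out-of-pocket cost, "controlling for salient covariates based on preliminary correlational analysis". Then: "We will repeat this analysis for implicit costs". The text gives no candidate list and no threshold. It does not say whether candidates are correlated with cost, with BPSD or with both, and no covariate is fixed.
- **Contrast (Analytic Plan, Phase 1 Aim 2):** there the covariates are named in advance, "controlling for age, sex and education".
- **Sample size (section 4a):** "Up to 40 Care Partners and their 40 care-recipients with ADRD will participate in this study".
- **Eligibility (section 4, Table 1, Care Partner):** "Lives with care recipient OR spends at least 4 hours/week with care recipient".
- **Implicit cost (section 5, Phase 2 Aim 2 measures):** "multiplying the average weekly hours of care provided by the CP by the average hourly wage of paid caregivers in Portland, Oregon", about $29.
- **Baseline data (Table 4):** the demographics item includes weekly hours of caregiving, so this variable is available to a screen.

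No significance level is stated for H1. The remark that significant findings are not expected stands under Phase 1 Aim 2 and is not repeated for Phase 2.

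**The concern.** A screen by sample correlation in about 40 dyads is noisy. A true confounder of ordinary size can fall below the cut-off by chance and be dropped. The two cost outcomes can end up with different covariate sets, and two analysts following the text could fit different models to the same data.

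Two variables deserve particular attention.

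- **Co-residence.** It varies by eligibility. It plausibly raises care hours, and so implicit cost, and also the number of behaviors a Care Partner sees and reports on the RMBPC. If it is left out, part of any BPSD-cost association may simply reflect contact time.
- **Baseline caregiving hours.** Implicit cost is hours times a constant wage, so a correlation screen is likely to pick this variable. Adjusting for it removes the variation that H1 is about.

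The estimates are meant to inform cost-efficacy and later trials. An association that is confounded, or adjusted away, would be carried forward.

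**Working it through.** **1. Is there a figure to reproduce?** No. The plan gives no alpha, power or error rate for H1. I assume a two-sided 5% level and n = 40. All confounder correlations below are assumptions.

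**2. The screen.** At n = 40, p<0.05 for a correlation means |r| > t/√(n−2+t²). With t = 2.024 on 38 df this is 2.024/√(38 + 4.097) = 0.312. A confounder correlated 0.25 with cost is kept in only 34-35% of samples. At 0.35 it is kept in about 62%, and at 0.40 in about 73%.

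**3. Simulation model.** There are q independent confounders Z, each with correlation a with BPSD and b with cost:

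- BPSD = a·ΣZ + √(1 − q·a²)·e₁
- cost = b·ΣZ + √(1 − q·b²)·e₂

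BPSD has no effect on cost. Candidates with |r| > 0.312 against cost are kept, cost is regressed on BPSD plus those kept, and p<0.05 for BPSD is counted. At 3,000 runs the simulation error near 5% is √(0.05 × 0.95/3000) = 0.4 percentage points.

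| Confounders (q) | a, b | Share of BPSD variance, q·a² | Screened | All confounders fixed |
|---|---|---|---|---|
| 1 | 0.3, 0.3 | 9% | 5.7% | 5.1% |
| 1 | 0.6-0.7, 0.3 | 36-49% | 6.5% | 5.3-5.6% |
| 3 | 0.25, 0.25 | 19% | 7.6% | 4.5% |
| 5 | 0.20, 0.20 | 20% | 9.8% | not run |
| 3 | 0.30, 0.30 | 27% | 10.4% | 5.4% |
| 5 | 0.30, 0.30 | 45% | 25.7% | 5.0% |
| 3 | 0.40, 0.30 | 48% | 14.0% | 4.5% |
| 3 | 0.45, 0.25 | 61% | 17.1% | 5.2% |
| 5 | 0.35, 0.25 | 61% | 31.3% | 4.8% |
| 4 | 0.40, 0.25 | 64% | 24.5% | 5.2% |

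The number of confounders and their joint strength matter more than any single correlation: five at 0.30 do far more damage than three at 0.30.

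**4. Sensitivity to what the plan leaves open.** With a single confounder, screening against BPSD or against both variables at p<0.05 gives 4.4-7.2%. A stricter cut of |r| > 0.5 gives 7-17%. With candidates that are pure noise and no confounding, the rate is 4.9-5.3%.

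**5. Fixing only part of the set.** If co-residence is fixed and the other confounders are still screened, three to five confounders leave 6-30%, depending on strength and on what is screened against. The fixed column above adjusts for every confounder in the simulation. It is what a set achieves when it contains the true ones.

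**6. Adjusting for caregiving hours.** Implicit cost = 29 × weekly hours; at the 4-hour eligibility floor this is 29 × 4 = $116 a week. If the same hours are used as covariate and outcome, the regression fits exactly, with coefficient 29 on hours and 0 on BPSD.

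If baseline hours correlate ρ with the hours used for cost, and relate to BPSD only through them, the standardised BPSD coefficient falls from r to r(1 − ρ²)/(1 − ρ²r²). Taking r = 0.4 and ρ = 0.9 as an illustration: 0.4 × 0.19/(1 − 0.81 × 0.16) = 0.076/0.870 = 0.09. Most of the association disappears.

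**The case against.** The strongest reply has four parts.

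- **The screen works well for the obvious confounder.** A reader might infer that co-residence confounding passes straight through, by comparing a regression without co-residence to one with it. The unadjusted regression is not what is planned. If co-residence is a candidate and is screened against cost at p<0.05, the rate stays at 4.6-5.7% for co-residence-cost correlations of 0.3 to 0.8, because a strong confounder is nearly always kept. This stands. What remains is that the plan does not name co-residence as a candidate.
- **The high rates depend on strong assumptions.** A reader might infer that the H1 test generally runs well above 5%. The documents do not support that: they name no confounders and give no correlations. In the 61-64% settings, using no covariates at all would reject 58-82% of the time, so screening removes most of the bias. This also stands.
- **Standard errors.** A reader might infer that screening makes them too small. The noise-only result of 4.9-5.3% gives no support for this; the inflation in the table is residual confounding.
- **H1 is associational and the study small.** H1 claims a relationship, not a causal effect, and an association produced by contact time would satisfy it literally. That weakens the language of false positives. It does not rescue the estimate, which is still described as controlled for covariates while its adjustment set is left to the sample.

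**Conclusion.** The concern holds in a limited form. The covariate rule is data-driven and unspecified in at most 40 dyads, although the same plan fixes covariates for Phase 1. The adjusted BPSD-cost estimates therefore depend on sample noise and analyst choice.

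The effect on error rates is small to moderate under mild confounding and large only under strong multiple confounding. No single inflated rate can be attributed to the plan, because the candidates, cut-off, alpha and correlations are all assumed here.

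The firmer grounds are structural: co-residence is not guaranteed a place in the model, and caregiving hours, nearly the implicit-cost outcome, could be selected into it. The second follows from the plan's own definition of implicit cost. How much association would be lost depends on how closely baseline hours match the hours used for costing, which the plan does not say.

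**What to change.** Replace the screening clause in Phase 2 Aim 2 with one pre-specified set, used for both out-of-pocket and implicit cost:

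- co-residence (yes/no), plus age, sex and education as in Phase 1, stating whose they are;
- dementia severity (MoCA) if a value at entry is available for all dyads. MoCA appears in Table 1 only as an eligibility threshold and is not in Table 4, and the exclusion of scores of about 15 or higher narrows its range.

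Also state that caregiving hours are excluded from the implicit-cost model, show the unadjusted estimate beside the adjusted one, and report H1 as an adjusted association with confidence intervals. Fixing co-residence while still screening the rest would not be enough.

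**Cost.** A few sentences of analysis text. Co-residence is established at eligibility and demographics are collected at baseline, so new data collection should not be needed. The set uses 4 degrees of freedom, or 5 with MoCA. With 40 dyads, an intercept and one BPSD term, residual degrees of freedom fall from 38 to 34 or 33. The set cannot protect against confounders it does not contain, and the report should say so.
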